4.4 Randomization

Patients will be randomized to either natural cycle frozen-thawed embryo transfer (group A), or hormonal replacement therapy cycle frozen-thawed embryo transfer (group B). As mentioned above, patients will only be randomized if they meet the complete eligibility criteria. Randomization will be ensured using a computer-generated randomization list and allocation concealment by the use of sealed opaque envelopes in the centre (physician will neither have access to the randomization list nor to the envelopes, which will be opened by study nurses involved in the study).

4.5 Interventions

- Natural cycle FET (Group A)

Patients are asked to perform a blood sample, with evaluation of serum estradiol (E2), progesterone (P), luteinizing hormone (LH) and follicle stimulating hormone (FSH), on the first or second day of the menstrual cycle (day 1 is considered as the first day of fresh red blood loss before 12AM). If these serum hormonal values are considered basal for the beginning of the follicular phase, patients are asked to come back on day 10 to 12 of the cycle for blood sample and transvaginal ultrasound scan

in order to assess follicular growth. Depending on the values on day 1 or 2, the physician performing the daily monitoring can decide to perform an earlier examination if necessary.

The timing of ovulation is determined based on a combination of ultrasonography features (the presence of a dominant follicle and adequate endometrium) and endocrine hormonal values in serum blood samples. Ovulation is generally defined as an, at least, 180% increase of LH compared to the mean level in the previous 24h (Frydman et al., 1982).

Frozen-warmed embryo transfer will take place six days following the spontaneous LH surge. Another blood sample will be performed 12 days after embryo transfer measuring human chorionic gonadotrophin (hCG), progesterone and estradiol in order to assess the outcome of the FET cycle.

- Hormonal replacement therapy cycle FET (Group B)

Patients are asked to perform a blood sample, with evaluation of serum estradiol (E2), progesterone (P), luteinizing hormone (LH) and follicle stimulating hormone (FSH) on the first or second day of the menstrual cycle (day 1 is considered as the first day of fresh red blood loss before 12AM). If these values are considered basal for the beginning of the follicular phase, estrogen supplementation (Estradiol valerate, Progynova® 3x2mg/day) is started to induce proliferation of the endometrium. Blood sample and transvaginal ultrasound are thereafter performed ten to fourteen days later. If the endometrium is considered adequate (generally considered if triple line and above 6,5 mm thickness)(Liu et al., 2018), embryo transfer is scheduled on the sixth day of progesterone (vaginal micronized progesterone, Utrogestan® 2x200mg twice a day) supplementation.

If the endometrium remains inadequate on day 10-14, estrogen priming will be prolonged with a maximum of 14 days of additional estrogen supplementation. If hereafter the endometrium stays below 6,5mm the cycle will be cancelled.

Another blood sample will be performed 12 days after embryo transfer measuring hCG, P and E2 in order to assess the outcome of the FET cycle.

In case of a positive pregnancy test, estrogen and progesterone supplementation will be continued until 8 weeks of gestation (in line with the onset of the luteo-placental shift) (Scott et al., 1991).

In case of escape spontaneous ovulation embryo transfer will be performed considering the presumable time of ovulation.

5. Treatment

- Group A: NC FET

In this group, no medication will be administered to the patients. The aim of this protocol is to detect the occurrence of a spontaneous LH surge in order to calculate the day of embryo transfer.

- Group B: HRT FRET

Estradiol valerate (Progynova[®], Bayer-Schering Pharma AG, Berlin, Germany) will be started on the first or second day of the menstrual cycle, in case of basal hormonal conditions, at a regimen of 2mg thrice a day. After ten to fourteen days of estrogen supplementation a check-up is planned with a blood sample and transvaginal ultrasound. If the endometrium is adequate (as above mentioned) transfer of the frozen-thawed embryo is planned on the sixth day of progesterone supplementation. We will use micronized progesterone vaginally (Utrogestan[®], Besins International) two capsules of 200 mg twice a day.

HRT cycles, using a consecutive administration of estrogen and progesterone, are used worldwide especially due to the advantage of easy and flexible scheduling and minimal monitoring which reduces the visits to the hospital compared to NC FRET. Although the universal use of HRT protocols in fertility centres no consensus is yet established concerning the ideal duration, route of administration or type of drugs used in order to prepare the endometrium for embryo transfer (Glujovsky et al., 2010).

We will adopt the above-mentioned protocol which is in line with the local protocol applied in the Centre of Reproductive Medicine in Brussels.

6. Data collection and Management

5.1 Statistical analysis

Continuous variables will be analyzed using the independent *t*-test or Mann–Whitney *U*-test depending on the normality of the distribution. Normality will be examined by the use of the Shapiro–Wilk test. Categorical variables will be analyzed by Pearson's chi-squared test or Fisher's exact test, as appropriate. To identify characteristics that may be related with the miscarriage rate, multivariate logistic regression analysis will be performed with the miscarriage rate as the dependent variable and transfer policy (NC versus HRT) as the main independent variable. Candidate variables considered for the analysis are: age, BMI, indication of infertility, percentage of patients with at least one top quality embryo and outcome of the previous fresh attempt. All candidate variables will be simultaneously entered into the logistic regression model. All tests will be two-sided with a level of significance set at $p < 0.05$. Analyses will be performed using STATA 15.0.

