Cryopreservation of frozen-thawed embryos has become an indispensable procedure in reproductive medicine. Mainly, thanks to the development of the vitrification procedure and the improvement of embryo survival rates after thawing (*Rienzi et al., 2017; Loutradi et al. 2008*), pregnancy rates have substantially increased. Likewise, the implementation of a single embryo transfer policy to reduce multiple pregnancies without lowering cumulative delivery rates (*Peeraer et al., 2014*) has led to an increase in surplus embryos deriving from an ovarian stimulation cycle. Besides, freeze-all strategies have been adopted for an increasing number of indications, namely to avoid ovarian hyperstimulation syndrome (=OHSS), or for preimplantation genetic testing (=PGT) patients, or in case of late follicular progesterone (P) rise or in case of endometrium- embryo asynchrony (*Bosch et al., 2016; Roque et al., 2015; Healy et al., 2016; Devroey et al., 2011; Shapiro et al., 2008; Racca et al., 2018; Groenewoud et al., 2017*). These developments have led to an increase in the number of frozen-warmed embryo transfer (FET) cycles performed in fertility centres over the last decade.

Despite this growing importance, little is known about the optimal endometrium preparation protocol prior to embryo transfer (*Ghobara et al., 2017; Groenewoud et al., 2017*). The two most common used treatment regimens to prepare the endometrium for embryo transfer are the so called natural cycle (NC) and the hormone replacement therapy (HRT) cycle. In a natural cycle the endometrium undergoes structural changes caused by consecutive exposure to estrogens and progesterone derived from the growing follicle. The moment of embryo transfer is determined by the occurrence of the natural ovulation, meaning on the fourth day after luteinizing hormone (LH) surge for cleavage stage embryos and for blastocysts on the sixth day (*Mackens et al., 2017*). HRT protocols are using exogenous administration of estrogens and progesterone in order to mimic a natural cycle and therefore endometrial development. The advantages of this latter protocol are the easy scheduling and minimal cycle monitoring. So far, no RCTs have been performed comparing a true NC (without hCG administration) and an HRT cycle for FET. However, concerns are raising about the high miscarriage rates reported in HRT cycles (*Tomás et al., 2012; Hreinsson et al., 2016; van de Vijver et al., 2016; van de Vijver et al., 2017*).

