4.2 Selection of study population

The study population consists of all PGT patients who fulfil the following inclusion criteria:

- Age between 18 and 42 years
- BMI under 35 kg/m²
- Regular menstrual cycle pattern (i.e. 24-35 days cycle)
- First, second and third ICSI-PGT cycle
- First frozen embryo transfer cycle following a fresh ICSI-PGT attempt
- PGT with trophectoderm biopsy on day 5 of embryonic development
- Signed informed consent

The exclusion criteria involve:

- Oligo-amenorrhea
- Age above 43 years
- BMI above 35
- Contraindications for the use of hormonal replacement therapy

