5.2 Sample size calculation

Sample size calculation was performed using internal data of our centre considering early miscarriage rates (defined as miscarriage before 8 weeks of gestation). We observed in our PGT population in 2017 an early miscarriage rate per started FET cycle of 9,9% in the natural cycle group compared to 18,4% in the group using HRT.

Based on these results, 522 patients are required (261 in each treatment arm) to have an 80% chance of detecting, as significant at the 5% level, an increase in the primary outcome measure (early pregnancy loss) from 9,9% in the NC group to 18,4% in the HRT group.

7. Ethical consideration

The protocol will be submitted to the local Ethics Committee of UZ Brussel. Strict confidentiality of all personal and research data will be ensured. The recruiting centre will be required to sign a clinical trial agreement document detailing their commitment towards complying with the relevant laws, regulations, codes of practice and obligations to publication. There are no conflicts of interest.

No specific reimbursement will be given to patients participating in the study.

8. References

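### Does the adjusted logistic model in section 5.1 fail because a covariate is worded as a group percentage and the fresh-attempt outcome is undefined?

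*Protocol*

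**What the plan says.** Protocol section 5.1 plans chi-squared or Fisher's exact tests for categorical variables. It adds a logistic regression whose stated purpose is to find characteristics related to miscarriage, "with the miscarriage rate as the dependent variable and transfer policy (NC versus HRT) as the main independent variable". Besides age, BMI and indication of infertility, the candidate covariates are "percentage of patients with at least one top quality embryo and outcome of the previous fresh attempt". The entry rule is fixed: "All candidate variables will be simultaneously entered into the logistic regression model".

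Three other sections bear on the point:

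- Section 4.2 admits women in their first to third ICSI-PGT cycle, with day 5 biopsy, at the "First frozen embryo transfer cycle following a fresh ICSI-PGT attempt".
- Section 4.3 randomises after the fresh ICSI cycle, provided non-affected embryos are available.
- The background section names several reasons for freezing all embryos, among them "or for preimplantation genetic testing (=PGT) patients".

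The protocol does not define or code the outcome of the fresh attempt, and it does not say whether a participant could have had a fresh transfer. The statistical analysis plan is not at hand.

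**The concern.** A logistic regression needs one value per woman for each variable. A percentage of patients describes a group, so as a covariate it could only be one number per arm or one number overall. In the first case it duplicates the treatment indicator, and in the second it duplicates the intercept. With every covariate forced in, one term would have to be dropped, possibly the treatment term. The dependent variable is likewise called a rate.

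The fresh-attempt variable looks doubtful for another reason. If PGT patients have all embryos frozen, there was no fresh transfer and so no pregnancy outcome to record. If there was a transfer, a woman going on to a frozen transfer does not have a continuing pregnancy from it. If these values were treated as missing, a complete-case fit would lose women.

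This is the only adjusted NC versus HRT estimate in the protocol, and the trial is open label. Repairing the covariate list after outcomes are known would leave some freedom in the adjusted result.

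**Working it through.** **Inputs.** Section 5.2 gives 9.9% (NC) against 18.4% (HRT) and states "522 patients are required (261 in each treatment arm) to have an 80% chance of detecting" this difference, "as significant at the 5% level". Section 5.1 makes all tests two-sided, and section 4.1 sets 1:1 allocation.

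**1. The plan's own figure.** The unpooled two-proportion formula is n per arm = (z0.975 + z0.80)² × [p1(1−p1) + p2(1−p2)] / (p2−p1)².

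- p1(1−p1) = 0.099 × 0.901 = 0.0892
- p2(1−p2) = 0.184 × 0.816 = 0.1501
- (p2−p1)² = 0.085² = 0.007225
- n = (1.960 + 0.842)² × 0.2393 / 0.007225 = 260.01, rounded up to 261 per arm, or 522

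The stated figure is reproduced. The formula contains no covariate, so the sample size does not depend on the logistic model. Expected events are 261 × 0.099 = 25.8 (NC) and 261 × 0.184 = 48.0 (HRT), 73.9 in all.

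**2. The percentage taken literally.** Let T be 0 for NC and 1 for HRT, and let the arm percentages be a and b. The covariate is then a + (b−a)T for every woman, a combination of the intercept and T. In a simulated data set of 522 women with intercept, arm, age, BMI and this term, the design matrix has rank 4 of 5. A single overall percentage is a multiple of the intercept, and the rank is again 4 of 5. Under the literal reading the term cannot be estimated.

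**3. The same item per woman.** Coded as at least one top quality embryo (yes/no), the matrix has rank 5 of 5 and the model fits on all 522. Section 4.3 randomises only once the fresh cycle is over and the embryos are known, so the indicator can be fixed before randomisation.

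**4. The fresh-attempt outcome.**

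- *Constant* (no one had a fresh transfer): adding a constant column gives rank 5 of 6. The term is redundant and is left out, and all 522 women stay in.
- *Varying*: the absence of a continuing pregnancy does not make the outcome constant. No transfer, a negative test, a biochemical loss, a miscarriage and an ectopic pregnancy are different values. Section 4.2 also admits second and third cycles, so earlier attempts may differ.
- *Not applicable for some*: this can be coded as its own category, and no woman is dropped.

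**5. Loss of women.** A loss arises only if the values are treated as missing and incomplete records are deleted. The protocol prescribes no such deletion and gives no share, so the figures below are pure assumption, with the loss taken as equal in both arms. The power is for the unadjusted comparison at the planned rates.

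| Assumed missing | Women left | Expected events | Power |
|---|---|---|---|
| 0% | 522 | 73.9 | 0.797 |
| 10% | 470 | 66.5 | 0.755 |
| 25% | 392 | 55.5 | 0.676 |
| 50% | 260 | 36.8 | 0.503 |

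At 80% missing, 73.9 × 0.2 = 14.8 events would remain, and at 100% none. An analyst who saw a covariate empty for most women would not delete them. The extreme rows describe a fit that no one would report.

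**The case for a change.** The best argument for acting is that the protocol does more than leave coding open. It names the variables and orders them all into the model. One of them is a group summary by its wording, and the dependent variable is not tied to either of the two miscarriage outcomes in sections 3.1 and 3.2. No single reading of the fresh-attempt variable is spelled out for every woman: if an earlier ICSI-PGT cycle is meant, first-cycle women have none. In an open-label trial it is better to settle such things before outcomes are seen, and a line of text costs little.

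The description of the wording stands: the percentage and the rate are group-level phrases, and the fresh-attempt variable is undefined. The consequences do not follow. Calling the outcome a rate is common shorthand, and section 3.1 defines the event, the loss of a clinical pregnancy before 8 weeks, which is also the outcome behind section 5.2. That no participant had a fresh transfer is an inference from a general background sentence. Variable coding and missing-data handling normally belong in a statistical analysis plan, which may already settle them.

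The obvious substitutes bring no clear gain. Quality of the transferred blastocyst is undefined for women without a transfer. Section 4.5 cancels HRT cycles when the endometrium stays inadequate, so that covariate would have gaps that arise after randomisation and may differ by arm. Replacing the fresh-attempt outcome with the ICSI-PGT cycle number is a preference, not a correction.

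**Conclusion.** No change to the plan follows. The percentage wording is a clerical slip with one sensible reading, and under that reading the model is estimable on all 522 women. The undefined fresh-attempt outcome is a gap that the analyst fills by coding categories, including one for no fresh transfer, or by leaving out a term that turns out constant. No loss of women or events is shown.

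The reach is small in any case. The model serves to identify related characteristics. The direct comparison of the arms falls under the chi-squared or Fisher tests in section 5.1, and the 261 per arm is reproduced without any covariate.

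This rests on three assumptions: embryo quality is recorded per woman, the outcome is scored for every randomised woman as the per-started-cycle rates in section 5.2 imply, and the coding is settled before outcomes are examined. Nothing in the protocol contradicts them.

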5.2 Sample size calculation

Sample size calculation was performed using internal data of our centre considering early miscarriage rates (defined as miscarriage before 8 weeks of gestation). We observed in our PGT population in 2017 an early miscarriage rate per started FET cycle of 9,9% in the natural cycle group compared to 18,4% in the group using HRT.

Based on these results, 522 patients are required (261 in each treatment arm) to have an 80% chance of detecting, as significant at the 5% level, an increase in the primary outcome measure (early pregnancy loss) from 9,9% in the NC group to 18,4% in the HRT group.

7. Ethical consideration

The protocol will be submitted to the local Ethics Committee of UZ Brussel. Strict confidentiality of all personal and research data will be ensured. The recruiting centre will be required to sign a clinical trial agreement document detailing their commitment towards complying with the relevant laws, regulations, codes of practice and obligations to publication. There are no conflicts of interest.

No specific reimbursement will be given to patients participating in the study.

8. References

